#### 286 **4.2 Inclusion Criteria**

- 287 • Diagnosis of myopia (ICD-10-CM Diagnosis Code H52.13)
- 288 • Refractive error meeting the following by cycloplegic autorefraction:
  - 289 • Myopia -1.00D to -6.00D spherical equivalent (SE) in both eyes
  - 290 • Astigmatism  $\leq$  1.50D in both eyes
  - 291 • Anisometropia  $<$  1.00D SE
- 292 • Complete eye exam with cycloplegic refraction within the past 12 months
- 293 • 5 to  $<$  13 years of age
- 294 • Parent understands the protocol and is willing to accept randomization to 380 nm light or control.
- 295 • Parent has a phone (or access to phone) and is willing to be contacted by Investigator's site staff.
- 296 • Relocation outside of the area of CCHMC site within the next 12 months is not anticipated.

#### 297 **4.3 Exclusion Criteria**

- 298 • Current or previous myopia treatment with atropine, pirenzepine or other antimuscarinic agent.
- 299 • Current or previous use of bifocals, progressive-addition lenses, or multi-focal contact lenses.
- 300 • Current or previous use of orthoK, rigid gas permeable, or other contact lenses being used to reduce  
301 myopia progression.
- 302 • Current or prior history of manifest strabismus, amblyopia, or nystagmus.
- 303 • Abnormality of cornea, lens, central retina, iris, or ciliary body.
- 304 • Prior eyelid, strabismus, intraocular, or refractive surgery.
- 305 • Down syndrome or cerebral palsy.

#### 306 **4.4 Sample Size**

307 Up to 72 participants will be enrolled in this study. Up to 24 will be enrolled into the three experimental  
308 groups:

- 309 • Violet light experimental group with polycarbonate glasses

- 310       • Violet light experimental group with CR-39 glasses
- 311       • Non-violet control group with CR-39 glasses.

#### 312   **4.5 Historical Information**

313   Historical information elicited will include the following: date of birth, sex, race, ethnicity, current  
314   refractive correction, iris color (brown or not brown), parental history of myopia (0, 1, or 2 parents),  
315   current medication use, history of and current medical conditions, and myopia treatment history.

#### 316   **4.6 Survey to Determine Lighting Schedule**

317   To determine suitable dawn and dusk times for each participant, participants will be asked when they  
318   typically wake up, eat dinner, and sleep. Additionally, participants will be asked to detail their typical  
319   evening schedule and any activities that may negatively affect compliance.

#### 320   **4.7 Testing at the Enrollment/Randomization Visit**

321   Testing at the enrollment/randomization visit will include the following:

##### 322       1. Standard Refraction

323       The investigator may use his/her standard refraction technique (with or without cycloplegia) at any  
324       time during the visit to ensure that the participant meets eligibility criteria with respect to refractive  
325       correction as described in section 2.5.

##### 326       2. Cycloplegic Autorefraction

327       Combination Drops (tropicamide 1%, cyclopentolate 1%, phenylephrine 2.5%) – one drop twice to  
328       each eye with 5 minutes between drops. The use of proparacaine prior to the cycloplegic drops is at  
329       investigator discretion. For each eye, three autorefraction measurements will be taken. For each  
330       measurement, the autorefractor will yield a final reading (either an individual reading or the  
331       mean/median of several individual readings, depending on the autorefractor) consisting of sphere,  
332       cylinder, and axis (see manual of procedures). Each final reading will be converted to a spherical  
333       equivalent refractive error (SER) and the mean of the 3 SER values for each eye will be used for  
334       confirming eligibility. A specific autorefractor model is not required for the study; however, each  
335       participant should have their autorefraction assessed using the same instrument during the entire  
336       study. The cycloplegic autorefraction should occur at 30 minutes  $\pm$  5 minutes from the time the  
337       second drop was instilled. If eyes are not sufficiently dilated/cyclopleged and/or if the  
338       dilation/cycloplegia has worn off before all cycloplegic procedures have been performed, another  
339       drop may be administered, followed by an additional 30-minute wait before testing. The use of  
340       proparacaine prior to this cycloplegic drop is at investigator discretion.

##### 341       3. Axial Length Measurement and Additional Biometry

342       Axial length will be measured 3 times in each eye using optical biometry (e.g., IOLMaster, LENSTAR).  
343       The following will also be measured 3 times in each eye using optical biometry (e.g., IOLMaster,  
344       LENSTAR) at the same time as axial length.

- 345       • Mean corneal radius (mm to 100th)

- 346 • Anterior chamber depth (mm to 100th)  
347 • Lens thickness, if available (mm to 100th)

348 A specific instrument is not required for the study; however, each participant should have axial  
349 length and additional biometry assessments made using the same instrument during the entire  
350 study.

351 If the Enrollment Visit occurs at a time or location that the IOLMaster or LENSTAR is unavailable, the  
352 Axial length measurement may be completed at the Equipment Pickup Visit.

#### 353 4. Optical Coherence Tomography Angiography (OCTA)

354 OCTA will be utilized to image retinal vasculature. 3 x 3 mm OCT angiograms will be obtained for  
355 each eye.

356 OCTA will be performed using the Heidelberg HRA2 Spectralis device (Heidelberg Engineering,  
357 Germany). Using a standardized scanning protocol of 15 degree field of view, 4.4 x 2.9-mm X by Y  
358 dimension on the retina, 256 B-scans (12 µm between B-scans), a Z-dimension of 1.9 mm (496 pixels  
359 approximated to 3.87 µm/pixel), and automatic real-time tracking (ART) of 5; patients will be imaged  
360 with macular area OCTA images of superficial vascular complex, deep vascular complex,  
361 choriocapillaris and choroid, centered at the fovea.

362 If the Enrollment Visit occurs at a time or location that the Heidelberg HRA2 Spectralis Device is  
363 unavailable, the OCTA may be completed at the Equipment Pickup Visit.

#### 364 4.8 Refractive Correction

365 To be eligible for randomization, the participant must be wearing refractive correction in each eye  
366 (single vision eyeglasses or soft, daily wear single vision contact lenses with any necessary  
367 adjustment for contact lens rotation and vertex distance) that meets the following criteria:

- 368 1. Myopia (by spherical equivalent) in both eyes must be corrected to within  $\pm 0.50$  D the  
369 investigator's cycloplegic measurement of refractive error.
- 370 2. Cylinder power in both eyes must be within  $\pm 0.50$  D of the investigator's standard refraction  
371 technique, which can be based on a cycloplegic or non-cycloplegic refraction.
- 372 3. Cylinder axis for both eyes must be within  $\pm 5$  degrees of the axis found on the investigator's  
373 standard refraction when cylinder power is  $\geq 1.00$  D or within  $\pm 15$  degrees when the cylinder  
374 power is  $< 1.00$  D.

375 Measurement of refractive error for assessing the above criteria may be performed as an over  
376 refraction or without refractive correction. If the participant meets all eligibility criteria, but their  
377 current correction does not meet the requirements for randomization, then new refractive  
378 correction (or a change in refractive correction) can be prescribed to meet the requirements. A new  
379 (or change) in refractive correction can also be prescribed if the investigator elects to change a  
380 smaller amount of refractive error, but the resulting prescription must meet the criteria above. The  
381 prescribed correction can be single vision eyeglasses or contact lenses. Single vision lenses will be

382 paid for by the study; contact lenses will be at the participants' own expense. A pair of eyeglasses is  
383 recommended for all participants and may be ordered through Zenni by the study team.

## 384 **5. Randomization**

### 385 **5.1 Randomization Process**

386 Participants eligible for randomization will be randomly assigned in a 1:1:1 distribution respectively to:

- 387 • Violet light experimental group (BIOS SkyView Lamp) with polycarbonate glasses
- 388 • Violet light experimental group (BIOS SkyView Lamp) with CR-39 glasses
- 389 • Non-violet control group (Aooshine Bedside Lamp) with CR-39 glasses

390 The investigator will construct a separate Master Randomization List using a permuted block design  
391 stratified by the treatment group. A participant is considered randomized when REDCap randomization  
392 process is completed.

393 The participant, parents, testers, and investigators will be masked to treatment group. If the need arises,  
394 the investigator may become unmasked after discussion of a specific case with the study team in  
395 response to any adverse events. The study coordinator will remain unmasked to the treatment group in  
396 order to facilitate the type of equipment and lenses the participant will need.

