#### 477 **7.5 Non-Randomized Treatment Other than Refractive Correction**

478 Non-randomized treatment for myopia other than changes in refractive error as described above is not  
479 permitted during the study. The investigator must call the principal investigator to discuss the case and  
480 obtain approval for an exception prior to initiating non-randomized treatment (including OrthoK, rigid  
481 gas permeable, and other contact lenses being prescribed for myopia management).

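### Section 5.1 stratifies by the arm being assigned and gives the randomisation list to a role it also masks, with no safeguard stated

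*Protocol*

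**What the plan says.** On the list, Section 5.1 reads: "The investigator will construct a separate Master Randomization List using a permuted block design". The sentence continues: "stratified by the treatment group. A participant is considered randomized when REDCap randomization" is finished. Allocation is 1:1:1 to three arms. No baseline stratification factor is named there or elsewhere in the protocol.

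On masking, the next paragraph reads: "The participant, parents, testers, and investigators will be masked to treatment group". If the need arises, "the investigator may become unmasked after discussion of a specific case with the study team in" response to adverse events. The study coordinator is the one role that stays unmasked, in "order to facilitate the type of equipment and lenses the participant will need".

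On what the investigator does, Section 4.7 (item 1) lets the investigator refract at any "time during the visit to ensure that the participant meets eligibility criteria with respect to refractive" correction. Section 4.8 judges readiness for randomisation partly against the "investigator's cycloplegic measurement of refractive error". Section 9.3 says that the participants are patients whom the investigator or colleagues already see. Section 7.5 shows that the title covers more than one person: "The investigator must call the principal investigator to discuss the case and" obtain approval for an exception.

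On group labels, the study design section (A, Study Groups) numbers the arms: group 1 is violet light with CR-39, group 2 violet light with polycarbonate, group 3 control light with CR-39. Section 2.1 describes study group 2 as the CR-39 group and attaches to that assignment a verbal reminder about the lower impact resistance of the lenses.

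**The concern.** A stratum has to be known before a participant is assigned, and treatment group is known only afterwards. The wording therefore cannot be carried out as written. A baseline factor may have been intended and lost, or the phrase may only mean balance across arms; the text does not say which.

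The second problem matters more. The person who writes an uncoded list holds the whole sequence, yet the protocol gives that task to a role that it masks a few lines later. If the list-maker also enrols or examines, the next allocation can be known before eligibility is confirmed. Whether and when a child is enrolled could then depend on the arm that comes next, and that examiner would not be masked during follow-up.

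The group 2 label is a separate matter. It decides which families hear the reminder. Because the reminder follows assignment and discloses lens type, it also sits badly with the statement that parents are masked.

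**Working it through.** No power or bias calculation applies. The check sets the statements side by side and counts participants.

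**1. Planned total.** Section 4.4 gives up to 24 in each of three groups: 3 × 24 = 72. This matches the stated maximum of 72 and the 1:1:1 ratio, so no figure in the plan changes.

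**2. The stratum.** Taken literally, stratifying by treatment group gives three strata, each containing one arm. Within a stratum the probability of that arm is 1, where 1:1:1 randomisation requires 1/3. Nothing would be randomised. With the phrase removed, a 1:1:1 permuted-block list can be built. Section 4.5 collects baseline history but links none of it to randomisation.

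**3. Who may know the allocation (Section 5.1).**

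| Role | List | Masking |
|---|---|---|
| Investigator(s) | builds it | masked; unmasked only for a specific case after an adverse event |
| Study coordinator | not mentioned | unmasked |
| REDCap | its completion defines when a participant is randomised | not described as hiding the sequence |

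The author of an uncoded list knows 72 of 72 allocations at full enrolment, whatever the block size. REDCap could hide the next assignment from other staff, but not from the person who wrote the list.

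**4. Where that knowledge could act.** The investigator title covers the eligibility refraction (4.7), the refraction used to judge readiness for randomisation (4.8) and routine care of these patients (9.3). New correction may be prescribed before randomisation (4.8), so the timing of randomisation can also vary.

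**5. Who hears the reminder, at 24 per group.**

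| Reading of Section 2.1 | Hears it | CR-39 families missed |
|---|---|---|
| Group 2 as numbered in the study design | 24 polycarbonate families | 24 + 24 = 48 |
| By lens name, CR-39 | 24 + 24 = 48 CR-39 families | 0 |
| Second item in the unnumbered lists of 4.4 and 5.1 (violet with CR-39) | 24 CR-39 families | 24 (controls) |

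No numbering lets a single group 2 cover both CR-39 arms.

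**6. What lens type reveals.** CR-39 is worn in one violet arm and in the control arm, so a family that learns it has CR-39 can rule out one of three arms but cannot tell violet from control. Polycarbonate is worn only in a violet arm, so a family that knows it has polycarbonate knows its arm.

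**The case against.** - **The stratum phrase is editorial.** Three arms, 1:1:1 and permuted blocks are enough to build the list, and a lost baseline factor is conjecture. This stands as to harm. The statement is still wrong as written.
- **The masking conflict is conditional.** Several people hold the investigator title, so the list-maker may neither enrol nor examine, or the list may be coded. A statistical analysis plan or manual not shown here may say so. This stands in part: the text does not prove that concealment was broken. A separate list-maker would protect concealment, but the masking sentence covers investigators in the plural, so the wording would still clash unless the list is coded.
- **Harm is limited.** Refractive eligibility uses numeric limits on the mean of three autorefractor values, and the primary outcome is also cycloplegic autorefraction. This stands for measurement. It does not remove discretion over which families are approached and when.
- **The count of 72 is not an estimate of bias.** Correct. It describes what a list-holder knows, and 72 is a maximum.
- **The group 2 label is a different matter, and families are warned anyway.** The consent form already explains the CR-39 risk, and the reminder repeats its language. That lowers the stakes, and the label adds no weight to the Section 5.1 point. The two sections still contradict each other.
- **The reminder does not unmask the main comparison.** For CR-39 families this is right (step 6). It still discloses lens type, which Section 5.1 gives as part of the reason the coordinator must be unmasked.

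**Conclusion.** The concern holds and should be fixed. Section 5.1 names an impossible stratum and gives the list to a role that it masks, with no safeguard stated. Followed as written with an uncoded list, it leaves one investigator knowing up to 72 of 72 allocations. Whether this biases enrolment depends on whether that person also enrols or examines, which the protocol does not settle. The likely damage is to allocation concealment and examiner masking. The effect on measuring the primary outcome is probably small, and no size of bias can be derived from the document.

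The group 2 contradiction also holds, as a separate point. Depending on the reading, the reminder misses 48, 24 or none of the 48 CR-39 families, assuming full enrolment of 24 per group.

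**What to change.** In Section 5.1:

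- Remove treatment group as a stratification factor, or name the baseline factor that was meant.
- Have the list generated and loaded into REDCap by someone with no part in enrolling or examining participants, such as a statistician or REDCap administrator, so that each allocation stays hidden until it is made. If a separate list-maker or a coded list is already planned, say so.

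Separately:

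- Reconcile the study design section and Section 2.1 on which lens group 2 wears.
- Reconcile the reminder given on assignment with the statement in Section 5.1 that parents are masked.

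The cost is a few sentences of protocol text and a short task for someone outside enrolment and examination. REDCap is already in use. Sample size, visits and analysis do not change.

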#### 154 **1.5 Bios SkyView Lamps**

155 In order to effectively deliver violet light, the BIOS SkyView lamp will be used. BIOS lighting uses  
156 patented circadian lighting technology to produce the highest melanopic to photopic lux ratio for a given  
157 color temperature, translating to better equivalent melanopic lux for a lower correlated color  
158 temperature than other LEDs. The BIOS SkyView lamps are equipped with wavelength-specific LEDs,  
159 able to provide a full profile of violet light (385 nm) for the purpose of this study. The SkyView lamps  
160 have been approved by CCHMC for research use (assessment ID: 109744). The Aooshine bedside lamps,  
161 which will act as the control light source, have also been approved by CCHMC for research use  
162 (assessment ID: 133975).

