## 218 **1.8 Study Objective**

219 The purpose of this short-term, pilot, randomized trial is to investigate the efficacy of violet light  
220 exposure through the BIOS SkyView Lamps at dawn and dusk versus non-violet light exposure through  
221 Aooshine Bedside Lamps in slowing the progression of myopia in school aged children as an alternative  
222 to current clinical treatments to determine whether to proceed to a full-scale longer-term randomized  
223 trial. This decision will be based primarily on assessing responses to light exposure by comparing  
224 treatment groups on the following outcomes:

- 225 • Axial length elongation
- 226 • Spherical refractive error
- 227 • Quality of life
- 228 • The proportion of participants reporting adverse effects
- 229 • The proportion of participants reporting >75% light exposure compliance

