## 237 **2. Considerations**

### 238 **2.1 Risks**

239 Safety testing of both the BIOS SkyView lamp and the Aooshine Bedside Lamp was completed via  
240 Underwriter Laboratories. (Document: QOVZ.E516890). Both the SkyView lamp (assessment ID: 109744)  
241 and the Aooshine Bedside Lamp (assessment ID: 133975) have both been approved for IRB study use by  
242 CCHMC.

243 There is a risk associated with wearing CR-39 lenses, as they are not as impact resistant as polycarbonate  
244 (mechanical strength class S vs F, respectively). Parents and participants will be educated on the risk via  
245 the consent form and encouraged to either remove eyeglasses or wear different eyeglasses for activities  
246 where there is a strong risk of impact to eyeglass lenses (i.e. sports). If participants are assigned to study  
247 group 2 (CR-39 lenses throughout the day), parents and participants will be reminded verbally of this risk  
248 using the language present in the consent form.

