### 429 **7.2 Telephone Calls**

430 Telephone calls will be made by the study coordinators to the participants and guardians at 2 weeks ( $\pm$  3  
431 days), 3 months ( $\pm$  1 month), and 9 months ( $\pm$  1 month) post Equipment Pickup visit.

432 Coordinators will contact parents to confirm that the BIOS SkyView/Aooshine lamp is working properly,  
433 encourage compliance, and question the parent as to whether the child is experiencing any issues with  
434 treatment.

435 Additionally, these calls will help maintain direct contact with the parents of the participants, develop  
436 and maintain rapport with the family, and assist with scheduling of study visits if needed.

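### Section 5.1 says participants and parents are masked, but the violet and control arms take home two different named lamps and no concealment is described

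*Protocol*

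**What the plan says.** Protocol 5.1 reads "The participant, parents, testers, and investigators will be masked to treatment group. If the need arises" and goes on to let the investigator be unmasked over an adverse event. The study coordinator stays unmasked in order to issue equipment.

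The same section lists the arms by lamp and lens. Two of them are "Violet light experimental group (BIOS SkyView Lamp) with CR-39 glasses" and "Non-violet control group (Aooshine Bedside Lamp) with CR-39 glasses"; the third is the BIOS lamp with polycarbonate lenses. Section 1.5 presents the Aooshine lamps as a separate product, "which will act as the control light source, have also been approved by CCHMC for research use".

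Other sections bear on what families know:

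- **4.2:** the parent must understand the protocol and be "willing to accept randomization to 380 nm light or control".
- **6.2 and 6.4:** the coordinator teaches the family to set up the lamp, and the child spends at least an hour with it at dawn and again at dusk.
- **2.1:** after assignment to CR-39 lenses, "parents and participants will be reminded verbally of this risk". The risk is the lower impact resistance of CR-39.
- **7.2:** "Coordinators will contact parents to confirm that the BIOS SkyView/Aooshine lamp is working properly". The same calls encourage compliance and ask about problems with treatment.

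Section 1.8 bases the decision on a full-scale trial on five outcomes. One is "The proportion of participants reporting adverse effects". The others are axial length, refractive error, quality of life, and the share reporting more than 75% compliance.

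**The concern.** A masking statement is a factual claim about trial conduct. Here the treatment is delivered by a visible object in the child's room, and that object differs between the violet and control arms. If families can tell which lamp they have, 5.1 describes a protection that the design does not provide, and a report repeating it would mislead.

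Knowledge of the arm could change what families say (adverse effects, survey answers) and what they do (how long the child stays with the lamp). The unmasked coordinator makes the calls that encourage use and ask about problems, so encouragement and questioning could also differ by arm. These outcomes feed the decision in 1.8 and 9.2.

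**Working it through.** This is mainly a consistency check. The only figure to reproduce is the sample size: 3 arms × 24 = 72, which agrees with 4.4.

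**Step 1. What each item reveals.** From the Study Design section (1.7 in the table of contents, 4.9 in the body), part A:

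| Group | Lamp | Lens |
|---|---|---|
| 1 | BIOS SkyView | CR-39 |
| 2 | BIOS SkyView | polycarbonate |
| 3 | Aooshine | CR-39 |

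- Lamp splits {1, 2} from {3}. That is exactly the violet versus non-violet contrast of 9.1, with 24 + 24 = 48 against 24.
- Lens splits {1, 3} from {2}. CR-39 alone does not separate violet from control; polycarbonate implies violet.
- Lamp and lens together give three distinct pairs for three arms, so the exact arm can be identified.

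**Step 2. What conceals the lamp.** Sections 1.5, Study Design, 5.1, 6.1 to 6.4 and 7.1 to 7.3 describe the lamps and their use. None mentions a shared casing, removal of branding, or a SkyView with its violet LEDs switched off as control.

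**Step 3. What the lens reminder adds.** Section 2.1 discloses the lens after assignment, but only to CR-39 families. Polycarbonate families could at most infer theirs from hearing nothing. The sentence also calls the CR-39 group study group 2, whereas Study Design makes group 2 the polycarbonate arm. Until these are reconciled, it is unclear which families hear the reminder.

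**Step 4. Which outcomes are exposed.**

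- *Adverse effects:* elicited by questioning families (7.2, 7.3, 9.3). Clearly exposed.
- *Compliance:* two sources, the daily parent survey (7.1) and the HOBO sensor (Study Design C, 7.3). The survey is exposed to reporting. The sensor is not, but the behaviour it records can change.
- *Quality of life:* no instrument or respondent is named. Exposed if families report it.
- *Refraction by cycloplegic autorefraction, and axial length:* instrument readings, less exposed while the tester stays masked.

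**Step 5. Illustration of scale.** The rates, the shift and the test are assumptions; none is in the protocol. Suppose the true rate is equal in both groups, controls report at rate p, and violet families report at p + b. With 24 controls and 48 violet participants, the chance of a false difference is the sum over i and j of Bin(i; 24, p) × Bin(j; 48, p + b), taken where a two-sided Fisher exact test gives a p-value of at most 0.05.

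| p | b = 0 | b = 0.10 | b = 0.20 |
|---|---|---|---|
| 0.10 | 0.029 | 0.126 | 0.428 |
| 0.20 | 0.033 | 0.107 | 0.367 |
| 0.50 | 0.039 | 0.101 | 0.318 |

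A shift of 10 points raises the false-difference rate from about 0.03–0.04 to 0.10–0.13, and 20 points to 0.32–0.43. The table shows sensitivity to a reporting shift. It does not show that a shift will occur.

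**The case against.** A reader might infer that the trial is effectively open-label. The document does not establish that. Each family sees one lamp with no comparator. Nothing says families are told which product emits violet, what labels the lamps carry, or that the light looks different. Section 1.5 gives the emission as 385 nm, near the lower edge of the 380–450 nm band in 1.6. The two product names in 7.2 may be staff-facing only. Accepting violet light or control under 4.2 shows that parents know the contrast, not their own assignment. The consent form is not available. This stands: actual unmasking is an inference. What remains is that the claim of masking has no described means behind it.

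A reader might also infer that three of the five outcomes in 1.8 rest on family report. Only adverse effects clearly do. Section 7.3 defines the compliance assessment by sensor data and 7.1 makes the survey a second source. The respondent for quality of life is unstated, and 9.1 and 9.2 do not name that outcome. The count of three is therefore not supported.

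Other limits also stand. The CR-39 reminder, if given in both CR-39 arms, does not separate violet from control. Nothing says the two lens materials look different, so the idea that a tester reads the arm from the child's glasses is speculation. The primary outcome is instrument-measured, 9.2 already puts the primary and secondary outcomes first, and 7.5 bars other myopia treatment without approval. The coordinator's unmasked role is declared with a reason.

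None of this supplies the missing concealment. Who is masked is a protocol statement, made here in 5.1, and cannot be left to an analysis plan.

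**Conclusion.** The point holds in a limited form. Masking of participants and parents is asserted in 5.1 but unsupported: lamp identity maps one-to-one onto the violet versus control contrast for all 72 planned families, and no concealment is described. Section 2.1 also discloses the lens to CR-39 families, under a group label that conflicts with Study Design.

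Reported adverse effects are clearly exposed, as are survey compliance and any family-reported quality of life. Sensor-recorded use could be affected through behaviour. Autorefraction and axial length are less exposed, so the primary comparison is not where the main risk lies.

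The conclusion assumes that the two products can be told apart by a family that knows what is being tested. The amount of bias cannot be derived from the document. The text of 5.1 needs correcting before the trial is described as masked.

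**What to change.** 1. **Section 5.1.** State how lamp identity is concealed, if it is. Otherwise state that families and the coordinator are not masked to lamp (or to lens where disclosed), and that masking applies to the testers who do autorefraction and biometry.
2. **Section 2.1.** Reconcile the group label with Study Design, and say which families receive the lens reminder.
3. **Section 7.3.** Tell families not to discuss equipment with testers. Have the coordinator collect the sensor and handle equipment questions away from them. If the glasses are taken from the child, do it only after distance acuity, near acuity and accommodation, which are tested in current correction.
4. **Section 7.2.** Use one identical call script in all arms for compliance encouragement and adverse-effect questions.
5. **Section 9.2.** Treat reported adverse effects, survey compliance and any family-reported quality of life as unmasked evidence. Rest the efficacy part of the decision on spherical equivalent refraction and axial length.

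The cost is protocol wording, a visit-order instruction and one script. The downside is that, unless concealment can be shown, the trial can no longer be described as participant-masked.
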